9.4.2 Rare adverse events during the study

As with any medication, rare side effects cannot be excluded.

9.4.3 Antidotes

Specific antidotes against rhC1INH do not exist. For allergic reactions appropriate standard treatment regimens indicated by the clinical situation (e.g. epinephrine, antihistamines, corticosteroids, etc) will be administered.

9.5 Description and justification of route of administration and dosage

Ruconest has been developed and was approved in the 27 EU countries plus Norway, Iceland, Liechtenstein and Israel for the treatment of acute attacks of angioedema in adult patients with HAE due to C1 inhibitor activity deficiency. Because C1INH is a plasma glycoprotein, an intravenous route of administration has been chosen.

[figure not shown]
The efficacy of Ruconest was demonstrated in two independently conducted RCTs in North America (Study C1 1205-01 RCT) and in Europe (Study C1 1304-01 RCT). The current study will provide further data on the safety and immunogenicity of Ruconest at a dose of 50 U/kg when used for the treatment of acute angioedema attacks in 2-13 year old HAE patients.

Ruconest, at the dose of 50 U/kg body weight (and with a maximum of 4200 U), will be administered by slow intravenous injection over a period of approximately 5 minutes. This dose and method of administration appeared safe and well tolerated in previously treated patients with HAE, including 16 adolescent patients.

9.6 Preparation and labeling of Investigational Medicinal Product

The Ruconest treatment solutions will be prepared from vials containing 2100 U of lyophilized rhC1INH. Each vial will be labeled and packed in a box. Ruconest will be labeled in accordance with regulatory requirements as follows:

Sample of outer package label:

Sample of vial label:

| | | |
|--|----------------------------------------------------------------------------------------------------------------------------------------------------------------------------------------------------------------------------------------------------------------------------------------------------------------------------------------------------------------------------------------------------------------------------------------------------------------------------------------------------------|--------------------------------------------------------------------------------------------------------------------------------------------------------|
| | 
Recombinant human C1 Inhibitor (rhC1INH) Protocol Nr.: C1 1209 Property of Pharming Technologies B.V. - T: [name] [name], The Netherlands Batch Nr.: XXXXX - Expiry date XX/XXX/XXXX Lyophilized powder. For intravenous infusion. 2100 U/vial - Reconstitute with 14 mL WFI For clinical trial use only To Be Used By Qualified Investigator Only Investigator; XXXXXXX Store at 2-25 °C (35.6-77°F)
 | 
Clinical trial C1 1209 Pharming Technologies B.V. Subject initials: X X X
 
Subject number: X X X X X
 |
|--|----------------------------------------------------------------------------------------------------------------------------------------------------------------------------------------------------------------------------------------------------------------------------------------------------------------------------------------------------------------------------------------------------------------------------------------------------------------------------------------------------------|--------------------------------------------------------------------------------------------------------------------------------------------------------|

Each vial containing the lyophilized material will be reconstituted with 14 mL water for injection (WFI) prior to use.

The preparations will be dispensed at the investigator's clinical center or by the hospital pharmacy of each investigational center with labels containing information similar to the sample label above.

For detailed pharmaceutical instructions, see [Appendix E](#).

9.7 Drug accountability

All study medication will be stored at the responsible investigator's clinical center and/or the Department of Clinical Pharmacy of the various hospitals. Drug accountability will be performed and monitored according to ICH-E6(R1) "Guideline for Good Clinical Practice".

As this study involves i.v. administration of the study medication administered by study personnel, patient compliance measures are not necessary. Study medication will be administered under direct supervision, according to the center's standard operating procedures. Two members of the center clinical staff (who should include at least one physician) will check the medication label for agreement with the study number and the patient's identity. Information with respect to volume of prepared and infused study medication will be documented.

10 METHODS

10.1 Study parameters

10.1.1 Main study parameter

The primary objective is the assessment of safety and tolerability.

This will be evaluated by recording of adverse events (spontaneously reported by the patient or observed by the investigator).

Immunogenicity (for all attack treatments) will be evaluated by the following parameters:

- antibodies against host related impurities (anti-HRI)
- antibodies against recombinant human C1INH (IgG and IgM) anti-rhC1INH)
- IgE antibodies against rabbit epithelium (anti rabbit epithelium IgE)

10.1.2 Secondary study parameters

At the first attack, pharmacokinetic and pharmacodynamic parameters will be evaluated for:

- C1INH activity and C4.

The following parameters will be determined: baseline level; C_{max} ; dose-normalized C_{max} ; T_{max} ; AUC above baseline; dose-normalized AUC; clearance; volume of distribution; elimination half-life ($t_{1/2}$); V_{max} ; K_m .

Efficacy will be evaluated by

- time to beginning of relief assessed by using the overall severity VAS, defined as the first time point with a decrease of at least 20 mm with respect to baseline at any eligible location, with persistence at the next time point (see section [10.2.3](#))
- time to minimal symptoms assessed by using the overall severity VAS, defined as the first time point at which the overall severity VAS falls below 20 mm for each assessed location
- time to beginning of relief assessed by using the IS-score defined as the first time point with a decrease of at least 1 point on the IS-score (investigator assessment) compared to baseline, at any eligible location.
- time to minimal symptoms assessed by using the IS-score, defined as the first time point at which the IS-score is less than or equal to 1 point for all assessed locations

All terms are defined in the List of Definitions in [Appendix F](#). See [section 10.2.3](#) for a detailed description of these efficacy parameters.

10.1.3 Other study parameters

Safety variables after single and repeat treatment that will be subject to exploratory analysis:

- vital signs
- ECG
- Routine clinical laboratory parameters

Efficacy variables that will be subject to exploratory analysis:

- time to beginning of relief based on questions 1 and 2 of the TEQ, defined as the first time-point at which Question 1 is answered as a little better, better or much better and Question 2

Safety of Ruconest in 2-13 year old HAE patients

is answered as yes for the most severe eligible location, with persistence of these responses at the next time point.

- time to minimal symptoms on the basis of Question 3 of the TEQ, defined as the first time-point at which Question 3 is answered as yes for all locations
- time to complete resolution based on the time-point at which all symptoms at all locations have resolved
- therapeutic failure: A patient will be assessed as having had a therapeutic failure if any of the following occurs:
 - time to the beginning of relief of symptoms for the attack based on the overall VAS occurs later than 4 hours after baseline
 - within 4 hours after beginning of treatment administration and after beginning of relief the overall VAS increases again to a value of at least the baseline score
 - the patient has occurrence of HAE at a new location within 4 hours after achieving beginning of relief of symptoms
 - the patient taking any of the medications that may interfere with the assessment of the impact of Ruconest on efficacy measures, between the onset of the attack and prior to time of initial relief of symptoms including:
 - Narcotics
 - plasma-derived C1 inhibitor
 - Fresh frozen plasma
 - Bradykinin receptor antagonist
 - Analgesics
 - Anti-emetics
 - Non Steroidal Anti-Inflammatory Drugs (NSAIDs)

Any change in current and optional maintenance therapy (androgens and/or anti-fibrinolytics) from the time of the onset of the current attack is not allowed. The dosage of androgens and anti-fibrinolytics may not be increased earlier than 24 hours after the treatment with study medication.

For a detailed description and definition of used terms, see [Appendix F](#).

10.2 Study procedures

10.2.1 Assessment of safety

This section describes all safety measurements recorded in this study; procedures for eliciting reports of adverse events / inter-current illness are further described in protocol section [11.1](#).

10.2.1.1 General safety measurements

Vital signs including blood pressure (supine systolic and diastolic), pulse and body temperature), and ECG will be considered as general safety parameters.

10.2.1.2 Safety laboratory measurements

Hematology and biochemistry

Safety of Ruconest in 2-13 year old HAE patients

Samples for routine hematology and biochemistry assays will be collected prior to each infusion and at Day 28. The routine hematology and biochemistry assays will be performed by the clinical centre's local laboratory.

The samples will be analyzed for the following hematology parameters: ESR, hemoglobin, hematocrit, red blood cell count (RBC), MCV, MCH, MCHC, total white blood cell count (WBC), platelet count, differential WBC units, neutrophils, lymphocytes, monocytes, eosinophils and basophils.

The samples will be analyzed for the following biochemistry parameters: sodium, potassium, chloride, calcium, inorganic phosphate, total protein, albumin, glucose, creatinine, AST, ALT, LDH, blood urea nitrogen, bilirubin (total), alkalinephosphatase, Gamma-GT, uric acid, total cholesterol, HDL cholesterol, Triglycerides, CRP and amylase.

Pregnancy testing

For female patients capable of bearing children (i.e. postmenarcheal girls), a urinary pregnancy testing for hCG will be performed prior to each treatment with Ruconest. Alternatively, serum hCG may also be performed to test for pregnancy as mandated by the clinical centre and/or Ethics Committee or when urine is not produced.

10.2.1.3 Diagnostic tests, PK/PD and immunological analyses

Following collection, the samples will be kept and processed **at room temperature**. The eventual plasma aliquots should be immediately stored upright at or below -20 °C until shipment to QPS Netherlands BV, where sample analysis will be performed. Investigator manuals will be provided to each center detailing the procedures related to central laboratory sample handling and (dry ice) shipment.

Diagnostic assays

Blood samples for diagnostic assays will be collected at screening. The samples will be analyzed for the following parameters: C1INH activity, C1q, C4 and C1INH auto antibodies (IgM, and IgG anti-rhC1INH); C4 will also be analyzed at baseline of each attack.

PK/PD assays

Blood samples for PK assays will be collected prior to the first treatment, one blood sample directly following infusion (named T 5 min, from a vein in the contra-lateral arm) and another blood sample between 2-4 hours post-infusion. This sampling time points are considered the most useful schedule derived from modelling of adult data. The samples will be analyzed for C1INH activity and C4.

Immunogenicity

The presence of anti-C1INH IgG and IgM antibodies (tested against immobilized rhC1INH), and of antibodies against anti-HRI will be assessed. Cut-off values of each assay were previously determined using plasma samples from normal donors and hereditary angioedema patients not previously exposed to rhC1INH. Plasma samples found to have an antibody test result above the cut-off level of the assay will be tested in confirmatory assay(s):

- Plasma samples above cut-off for anti-C1INH antibody will be tested in an anti-C1INH displacement assay, to determine whether or not increased values observed in the ELISAs

Safety of Ruconest in 2-13 year old HAE patients

were due to specific or non-specific responses. Samples that are confirmed positive in the displacement assay will then be tested in an assay for neutralizing antibodies.

- Plasma samples that show a response above the cut-off level in the initial anti-HRI ELISA will be tested in a displacement assay.

These tests will be performed on samples obtained at screening, prior to each treatment with rhC1INH, and at the Day 28 and Day 90 follow up visits. If the new attack is treated before completing the follow-up visits for the previous attack, the D28 or D90 visit schedule will be reset based on the most recent treatment.

These tests and antibody assays mentioned above will be performed by QPS Netherlands B.V.

- C1INH activity will be determined as inhibitory activity against C1 esterase with a chromogenic assay.
- C1q assays will be performed by nephelometry. This assay will be performed at screening to confirm the diagnosis of HAE and/or to exclude AAE.
- Levels of C4 antigen will be determined by nephelometry. This will be performed at screening and at baseline of each attack to support the diagnosis of HAE.
- Anti-rabbit epithelium (dander) and anti-cow milk IgE assays will be performed using a validated, commercially available system⁽⁸⁾ (ImmunoCAP®, Phadia, Sweden; or equivalent. Prior to treatment with Ruconest a negative test for anti-rabbit epithelium (dander) (cut off <0.35 kU/L) should be documented. Anti-cow milk IgE will be tested once at screening. Anti-rabbit epithelium (dander) IgE will be performed at screening, at the Day 28 follow-up visit of each attack, every year following screening, and if adverse events are observed indicative of hypersensitivity reactions.

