6 STUDY DESIGN

This study is an open-label, Phase II, non-comparative clinical study in pediatric patients from 2 up to and including 13 years of age, with a confirmed diagnosis of HAE.

The study will continue until at least 20 patients have been administered with Ruconest for at least one acute HAE attack.

Patients will be eligible for treatment with Ruconest if they present to the clinic within 5 hours of onset with an acute attack of at least moderate severity IS of at least 3) without signs of spontaneous regression.

The patient will remain in hospital and closely monitored in the study center for at least 4 hours after study medication administration.

For safety evaluation, prior to and at Day 28 after study medication administration, a blood sample will be drawn for routine laboratory parameters. In addition to monitoring of vital signs (prior to and 30 min, 1, 2 and 4 hours after study medication administration), an ECG will be recorded prior to and between 30 minutes and 2 hours after study medication administration.

The evolution of the acute angioedema attack will be monitored by the administration of patient questionnaires (Visual Analog Scale (VAS) and Treatment Effect Questionnaire (TEQ)) at 30 min, 1, 2, 4, 8, and 24 hours, and the Investigator Score (IS) at 30 min, 1, 2 and 4 hours post study medication administration.

For PK/PD evaluation, blood samples will be collected prior to the first treated attack, and at 5 minutes and between 2 and 4 hours following the first study medication administration.

Four hours after study medication administration the patient may be discharged from the clinic if the investigator judges the patient's condition well enough. The investigator will schedule a telephone contact at 24h (\pm 4 hours) after study medication administration. Follow up visits are planned at D28 (\pm 3 days) and D90 (\pm 7 days).

Multiple attacks can be treated, provided there is a minimum 24 hour interval between subsequent treated attacks and with a maximum of 10, and as long as anti-rabbit epithelium (dander) IgE testing remains negative. Patients can therefore be treated beyond the age of 13.

A schedule of trial assessments can be found in [Appendix A](#).

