If a new attack is treated before completing the follow-up visits for the previous attack, the D28 or D90 visit schedule will be reset based on the most recent treatment. Multiple attacks can be treated, provided there is a minimal interval of 24 hours between subsequent treated attacks.

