7.3 Exclusion criteria

Screening

- A diagnosis of acquired C1INH deficiency (AAE)
- A medical history of allergy to rabbits or rabbit-derived products (including rhC1INH, antisera), or positive anti-rabbit epithelium (dander) IgE test (cut off>0.35 kU/L in ImmunoCap® assay (Phadia, Sweden) or equivalent)
- Treatment with investigational drug in another clinical study in the last 30 days
- Any clinical significant abnormality in the physical examination and/or the routine laboratory assessments, that in the opinion of the Investigator makes the patient unsuitable for participation in the study
- Patient or legal guardian whose decision to participate might be unduly influenced by perceived expectation of gain or harm by participation, such as patient or legal guardian in detention due to official or legal order
- Any condition or treatment that in the opinion of the investigator might interfere with the evaluation of the study objectives

Treatment

- Any changes since screening that would exclude patient based on above exclusion criteria.
- 10 HAE attacks were previously treated with study medication.
- Suspicion for an alternate explanation of the symptoms other than an acute HAE attack.
- Use of any disallowed concomitant medication since onset of acute HAE attack (see [Section 8.2.1](#)).
- Positive pregnancy test (urine or serum)

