10.2.4.2 Treatment Visit

An eligible patient may only be treated if the patient presents with an eligible attack. The patients will remain in hospital for 4-5 hours during a treatment visit. The procedures performed at subsequent treatment visits will be the same.

Permitted deviations of actual sampling and assessment time points from those projected in the Schedule of Assessments will be within ten percent, calculated from $t = 0$ (start of study medication administration) to the relevant activity. The following procedures will be performed over a 4-5 hour period as follows:

At presentation of the attack:

- assessment of current angioedema signs and evaluation of evolution since onset of symptoms, including investigator's symptom score
- perform physical examination (including weight), assessment Tanner Stage (see [Appendix G](#))
- record vital signs (supine blood pressure, pulse, body temperature)
- assess and record changes or additions in current prescription and OTC medications, vitamins and supplements including start date, dosage, frequency, route, indication for usage since the last study visit
- assess and record if any medications previously reported as taken on an as needed basis (PRN) were taken since the onset of symptoms
- record and assess new AE/SAE's or changes to ongoing AE/SAE's since the last visit or last infusion, if applicable
- evaluate all inclusion and exclusion criteria
- 12-lead ECG
- blood sampling for routine laboratory safety parameters, PK/PD (only at first attack) and Immunological Analysis (C1INH auto antibodies (IgM and IgG anti-rhC1INH and anti-HRI) and C4.
- pregnancy test (only for post-menarcheal female patients)
- assessment of baseline angioedema signs by VAS-scales and TEQ just before infusion.

Infusion (T=0h)

- perform infusion of Ruconest

Directly following infusion (T5 min)

- blood sampling for PK (from a vein in the contra-lateral arm)

30 minutes (\pm 3 min), and 1 hour (\pm 6 min), 2 hours (\pm 12 min) and 4 hours (\pm 24 min) post-Infusion

- assessment of current angioedema signs (patient's VAS, TEQ and IS-score)
- record vital signs (supine blood pressure, pulse, body temperature)
- 12 lead ECG between 30 min and 2 hours
- blood sampling for PK/PD between 2 and 4 hours post-infusion
- record and assess new AE/SAE's or changes to ongoing AE/SAE's since infusion
- record changes in concomitant medication and/or need for rescue medication

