Independent of the occurrence of eligible acute HAE attacks, a center visit is scheduled at every year (\pm 1 month) after screening at which the following procedures are scheduled:

- blood sampling for IgE antibodies against rabbit epithelium
- HAE history since previous visit, if applicable (e.g. occurrence of intercurrent HAE-episodes etc)
- record and assess new AE/SAE's or changes to ongoing AE/SAE's since the last visit, if applicable
- record changes in concomitant medication

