- (1) Catheter system to be used if possible, which can be used for blood sampling and treatment administration (and a second dose if necessary), and can be left for 4 hours. In order to minimize patient distress, local, topical anesthesia may be considered before placing a catheter.
- (2) P = at presentation with an acute angioedema attack. Assessments and blood samples should be done as close as possible to the time of treatment administration; the VAS and TEQ should be completed immediately prior to study medication infusion.
- (3) The patient may be discharged after 4 hours; in that case the patient questionnaire at T8h will not be completed during hospitalization but at home by the patient/legal guardian; the questionnaire is to be returned at the Day 28 visit.
- (4) Telephone interview regarding HAE-symptoms in order to document possible therapeutic failure, or late relapse, registering localization, severity and time course.
- (5) C1INH activity, C1q, C4, ant bodies against rhC1INH (confirmation + neutralizing antibodies); C4 will be repeated at baseline of each attack.
- (6) Anti rabbit epithelium (dander) and anti cow milk IgE testing at screening. Anti rabbit epithelium (dander) IgE only is tested at the Day 28 follow-up visit of each attack and every year after screening.
- (7) IgM and IgG ant bodies against C1INH (confirmation + neutralizing) and HRI (+confirmation), and C4 (only at screening and baseline of each attack)
- (8) C1INH activity (PK) and C4 (PD), only at first attack, at baseline, directly following infusion and one additional sample within the window of 2-4 hours
- (9) If relevant, i.e. only for post-menarcheal female patients

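### A child re-treated before the Day 28 visit has no scheduled anti-rabbit IgE test between the two treatments, although re-treatment depends on IgE staying negative

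*Protocol*

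**What the plan says.** **Condition for re-treatment.** Protocol section 6 lets further attacks be treated "as long as anti-rabbit epithelium (dander) IgE testing remains negative". Section 7.2 sets a 24-hour minimum since the last study treatment. Section 7.3 applies the screening exclusions, including a positive IgE, again at each attack. It also sets the cap, excluding a patient once "10 HAE attacks were previously treated with study medication".

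**IgE as an outcome.** Section 10.1.1 says "Immunogenicity (for all attack treatments) will be evaluated by the following parameters" and lists IgE against rabbit epithelium among them. SAP 4.2 lists it too.

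**When IgE is measured.** Section 10.2.1.3: "Anti-rabbit epithelium (dander) IgE will be performed at screening, at the Day 28 follow-up visit of each attack, every year following screening", and additionally after adverse events that point to hypersensitivity. Appendix A, footnote 6, agrees: "Anti rabbit epithelium (dander) IgE only is tested at the Day 28 follow-up visit of each attack and every year after screening". The yearly visit is fixed to the screening date (section 10.2.4.3): "Independent of the occurrence of eligible acute HAE attacks, a center visit is scheduled at every year".

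**What is sampled before each dose.** Section 10.2.4.2 specifies "Immunological Analysis (C1INH auto antibodies (IgM and IgG anti-rhC1INH and anti-HRI) and C4". IgE is not included.

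**What early re-treatment does.** Under section 6, "the D28 or D90 visit schedule will be reset based on the most recent treatment". SAP 2.2 adds that the earlier attack's Day 28 form is then partly completed from the diary.

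**Analysis.** SAP 6.8.8 summarises anti-rhC1INH IgG and IgM and anti-HRI by attack at Presentation, Day 28 and Day 90. SAP 6.9.1 handles IgE with individual listings and one shift table, from Screening to Day 28 of each attack.

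**The concern.** The plan makes re-treatment depend on a laboratory result and, for closely spaced attacks, schedules no sample that could supply it. Protocol 9.4.1 identifies allergic reaction as the one clinically important risk known so far. Section 11.2 makes a type I reaction from newly formed IgE to rabbit antigens an event of special interest.

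A child who converted silently after one treatment could be treated again, possibly several times, before any scheduled test showed it. The later positive result could not be assigned to a particular treatment. The 4-hour observation, the stopping rules and the event-triggered test all act only after a reaction.

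There is also a loss of data on the primary objective. Children re-exposed at the shortest intervals would contribute the fewest IgE results.

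**Working it through.** The plan gives no figure to reproduce. The check sets the schedule out for one case and then illustrates how often that case could arise. Here a treatment means the treatment of a separate attack, not the optional second dose within one attack.

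**1. Schedule for a second attack treated before Day 28 of the first**

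| Time point | Anti-rhC1INH IgG/IgM, anti-HRI | Anti-rabbit IgE |
|---|---|---|
| Screening | yes | yes |
| Presentation, attack 1 | yes | no |
| Day 28, attack 1 | moved to attack 2 | moved to attack 2 |
| Presentation, attack 2 | yes | **no** |
| Day 28, attack 2 | yes | yes |
| Day 90, attack 2 | yes | no |

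For the other antibodies, the sample at presentation of attack 2 replaces the lost Day 28 sample. For IgE nothing does, apart from a yearly test that happens to fall there.

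**2. Can the yearly test be relied on?** Ten treatments have 9 gaps. At 24 days each they span 9 × 24 = 216 days. The earliest first yearly visit, one year minus one month, is about day 335. If the first attack comes soon after screening, all 9 re-treatments could rest on the screening result.

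**3. Share of re-treatments with no intervening Day 28 test.** Assume treated attacks follow a Poisson process with a given rate per year. Then P(next treated attack within d days) = 1 − exp(−rate × d/365). The Day 28 window (section 10.2.4.3) is day 25 to day 31.

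| Treated attacks per year | d = 25 | d = 28 | d = 31 |
|---|---|---|---|
| 1 | 0.066 | 0.074 | 0.081 |
| 3 | 0.186 | 0.206 | 0.225 |
| 6 | 0.337 | 0.369 | 0.399 |
| 12 | 0.560 | 0.602 | 0.639 |

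In the case series cited in Protocol 4.1, 31% of patients had fewer than 1 attack a year, 23% had 1–5 and 46% had 6 or more. The rate of 12 is an assumption within that last group. If half of attacks are eligible and treated, 6 a year becomes 3 (19–21% for d = 25 to 28) and 12 becomes 6 (34–37%).

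**4. Per child.** Treatments per patient in the earlier open-label data (Protocol 9.3) were 168/62 = 2.7, 194/57 = 3.4 and, for adolescents, 50/16 = 3.1. Three treated attacks have 2 gaps, so P(at least one untested gap) = 1 − (1 − p)². For d = 25 and 28:
- 3 treated attacks a year: 1 − (1 − 0.186)² = 0.337 and 1 − (1 − 0.206)² = 0.369
- 6 a year: 0.560 and 0.602

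**5. Extreme case.** All 9 gaps untested has probability p⁹. This is 0.00006 to 0.00013 at 6 a year and 0.0055 to 0.0103 at 12 a year, before allowing for yearly tests.

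**The case against.** The strongest points on the other side are these.

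- **The remedy does not stop the second dose.** Samples are frozen and shipped to a central laboratory, and no turnaround time is given. In a cluster of two attacks, the second treatment would still be given without an IgE result from after the first. This stands. The gain for eligibility starts with the third treatment of a cluster, if the result is back. Otherwise the gain is in the data.
- **The protocol does ask for a documented negative test before treatment.** Nothing requires that test to be later than the last dose, so the screening result satisfies it. One can read the condition as the latest scheduled test being negative. On that reading the plan does not contradict itself, but it leaves the shortest re-exposure intervals unmonitored.
- **Clinical experience is reassuring.** The documented anaphylaxis was on first exposure, in a volunteer with undisclosed rabbit allergy. Laboratory data suggested that the one possibly related hypersensitivity event in the earlier open-label extension was not IgE-mediated. Weekly dosing of 25 patients led to no discontinuations. This limits the expected harm, but the documents do not say that IgE was tested serially in those studies.
- **Anti-HRI is sampled before every treatment.** That is relevant monitoring, but it does not measure IgE, which is the criterion for re-treatment.
- **The rates lean high.** The case series is not paediatric, and 54% of its patients (31% + 23%) had fewer than 6 attacks a year. Treatment also needs an investigator score of at least 3 and evaluation within 5 hours of onset. This is fair, so the percentages are an upper illustration.
- **The SAP cannot analyse samples that were not taken.** True. The gap starts in the protocol and the SAP inherits it.

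**Conclusion.** The concern holds. When a child is re-treated before Day 28, the plan as written provides no scheduled IgE test between the two treatments, outside a coincidental yearly visit. It also leaves no entry for the earlier attack in the only IgE table. This follows from the text and needs no assumption.

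How often it would occur does need assumptions: Poisson attacks, and a rate of treated attacks that the documents do not give for ages 2–13. Across 1 to 6 treated attacks a year, roughly 7% to 37% of re-treatments would be affected (day 25 to 28 cut-off), and up to 40% if the visit falls on day 31. Ten treatments resting on screening alone is possible but very unlikely. The documents report no IgE conversion after dosing, so this is a gap in monitoring and not evidence of harm. It should be fixed because it touches a primary-objective parameter and the change is cheap.

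**What to change.** Run the anti-rabbit epithelium IgE assay on the immunology sample already drawn at Presentation of every attack (Protocol 10.2.1.3, 10.2.4.2 and Appendix A, footnotes 6 and 7). State that the result arrives after the current dose, so it decides eligibility for later doses and enters the immunogenicity analysis but does not hold back the same dose. In SAP 6.9.1, add Presentation of each attack to the IgE shift table.

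The cost is one central assay per treated attack and a short amendment, with no extra visit or needle. Volume needs confirming with the central laboratory. The 1.8 mL Day 28 tube already serves IgG, IgM, HRI and IgE, but the 1.8 mL Presentation tube at later attacks also carries C4. If it is too small, the 2.7 mL tube used at the first attack adds 0.9 mL. In the protocol's 12 kg example (blood volume 960 mL) that is 0.9/960 = 0.09%. The whole draw, with 10 mL for safety tests, would rise from 11.8 mL (11.8/960 = 1.2%) to 12.7 mL (12.7/960 = 1.3%). It is already above the 1% single-draw guide cited in section 10.2.2, so the smaller tube is preferable if it suffices.
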